8.1.3 Prior and Concomitant Medication

All prior medications used within the last 30 days before Visit 2 (Day 1) Tc 99m tilmanocept administration through the Follow-Up Call will be documented.

8.2 Tc 99m Tilmanocept Preparation and Administration

Based on the dose cohort the subject is enrolled in, the dose of Tc 99m tilmanocept should be ordered from Cardinal Health once the subject has been scheduled for imaging.

In Nuclear Medicine, prior to IV injection and imaging, an indwelling catheter will be placed for venous access. The preferred site of IV placement should be the left or right antecubital vein. Other IV access sites are acceptable if access is problematic.

The filled syringe will be connected to the catheter for a slow push injection. Immediately after the completion of the injection, a 10 cc sterile normal saline flush will be administered. Injection of Tc 99m tilmanocept will be at study time 0:00.

For SC injection, the preferred site of placement is the ankle(s) or the dorsal surface of the foot (feet). Approximately 0.5 mL of the 1.0 mL prepared injection shall be administered to each the left and right leg. Injection of Tc 99m tilmanocept will be at study time 0:00.

8.3 SPECT/SPECT-CT Image Acquisition

The camera used to obtain the images should be a 2-headed SPECT or SPECT/CT camera equipped with a low-energy, high-resolution collimator with a 15% window (20% can be used if 15% setting not available) centered over a 140keV peak.

The camera must have passed the daily SPECT QC (quality control) tests as per the manufacturer's recommendation for that day's scan schedule.

Whenever possible, subject should be asked to void after injection and prior to the imaging session.

Subjects should be positioned supine with arms at their side. The subject's head, legs, hands, and hips should be in the true anterior position. The subject should be instructed to remain as motionless as possible during the scan and asked to breathe as shallowly as comfortable when the camera is passing over the chest. To help minimize leg motion, a light tape around the ankles can be used to keep the legs together. A pillow under the knees is often very helpful for comfort.

A whole body planar scan should be obtained at the following time points:

- 60-75 minutes post-IV/SC administration
- 4-6 hours post-SC injection

Optional SPECT/CT region(s) of interest scan(s) can be obtained at the following time points:

- 60-75 minutes post-IV/SC administration
- 4-6 hours post-SC injection

It is anticipated that the whole body planar scan would be acquired first for 25-30 minutes. Using a 2-headed camera (nominal 20" x 15" FOV [field of view]) a target of 5-7 million counts should be obtained for the summed view of both heads. For the higher activity injections, it may be possible to attain this target in a shorter time, allowing the subject more time off the bed between scans.

Following the whole body scan, optional SPECT/CT region(s) of interest scan(s) can be obtained. It is anticipated that a SPECT/CT scan would be acquired over 25-30 minutes. The use of a calibration syringe for each SPECT scan is not necessary. It is very important that the subject remain motionless for the duration of the complete SPECT/CT scan.

SPECT/CT slices will be reconstructed using the manufacturer's recommended reconstruction algorithms including the recommended attenuation correction.

It is strongly recommended that each site should perform all imaging acquisitions per their camera manufacturer and model parameters and in accordance with their institutional practices for both the whole body scan as well as the SPECT/CT imaging.

De-identified DICOM copies of all acquired images will be transmitted to Navidea Biopharmaceuticals. The areas of localization will be identified, documented and captured in the eCRFs.

8.4 Post-Injection and Imaging Biopsy Acquisition

The purpose of the KS lesion biopsy will be to determine the proportion of CD206-expressing cells and quantity of CD206 (IHC fluorescence) in KS tissues in parallel with an analysis of KS imaged with Tc 99m tilmanocept. A non-visceral site of KS for biopsy post-imaging in each subject will be chosen by the Nuclear Medicine physician based on visualized localization and lesion size. If no lesion is determined to localize Tc 99m tilmanocept, a lesion of at least 5-6 mm in a clinically accessible area will be biopsied as chosen by the Investigator(s) who will record selection and rationale.

All subjects will receive the biopsy on the day of IV Tc 99m tilmanocept administration at the completion of imaging.

A biopsy up to 6mm of the designated lesion will be taken, and a photograph of the biopsy site with a measurement scale will be taken and stored with the subject's research chart. The tissue will be obtained at the completion of Tc 99m tilmanocept IV injection and imaging and delivered on ice to the Department of Pathology at Zuckerberg San Francisco General Hospital. The biopsy will be sectioned into a formalin-fixed paraffin-embedded (FFPE) segment and a fresh or frozen segment to be used for other analyses. FFPE tissue sections will be quantified for CD206 and LANA through a standardized quantitative image analysis program. HHV8 will be quantified by qPCR.

8.5 Pharmacokinetics

No pharmacokinetic investigation will be performed in this study.

8.6 Safety

8.6.1 Adverse Events

8.6.1.1 Definition of Adverse Event

The definitions below follow International Conference on Harmonization (ICH) – Good Clinical Practice (GCP) (see also ICH Guideline for Clinical Safety Data Management: Definitions and Standards for Expedited Reporting).

Adverse Event (AE)

An AE is defined as any untoward medical occurrence in a subject administered a pharmaceutical product and which does not necessarily have a causal relationship with this treatment. An AE can therefore be any unfavorable and unintended sign (including an abnormal laboratory finding), symptom, or disease temporally associated with the use of a medicinal (investigational) product, whether or not considered related to the medicinal (investigational) product.

Any clinically significant change in a condition (worsening) from screening that results in a change in subject management will be considered an AE and will be recorded on the AE page of the CRF.

By definition for this study, all untoward medical occurrences beginning on the day of Visit 2 Baseline (Day 1) through the Follow-up Phone Call are to be reported as AEs. AEs continuing after study completion will be followed to normalization or stabilization. Additionally, untoward medical events occurring prior to the day of Tc 99m tilmanocept administration will be collected and added to the subject's medical history unless they are related to a study procedure, in which case the event will be recorded as an AE. SAEs will be reported from the time of consent through the end of participation.

8.6.1.2 Categories for Adverse Event Assessment

All AEs will be assessed and documented by the investigator according to the categories detailed below.

Seriousness

For each AE, the seriousness must be determined according to the criteria given in [Section 8.6.1.5](#).

Severity

The severity of an AE is classified according to the following categories, taking into account the possible range of the intensity of the event:

- Mild - The AE is transient and easily tolerated by the subject.
- Moderate - The AE causes the subject discomfort and interrupts the subject's usual activities.
- Severe - The AE causes considerable interference with the subject's usual activities and may be incapacitating or life-threatening.

Specific drug treatment

Any specific drug treatment will be documented.

Causal relationship to investigational product

The investigator will use the following definitions to assess the relationship of the adverse event to the use of investigational product:

Definitely related: Event can be fully explained by administration of the investigational product.

Probably related: Event is most likely to be explained by administration of the investigational product rather than the subject's clinical state or other agents/therapies.

Possibly related: Event may be explained by administration of the investigational product or by the subject's clinical state or other agents/therapies.

Probably not related: Event is most likely to be explained by the subject's clinical state or other agents/therapies, rather than the investigational product.

Definitely not related: Event can be fully explained by the subject's clinical state or other agents/therapies.

For causality assessments, events meeting the categories of definitely, probably, or possibly related will be considered to be related to investigational product.

Causal relationship to study procedure

The investigator will use the following definitions to assess the relationship of the adverse event to the study procedure:

Definitely related: Event can be fully explained by the study procedure.

Probably related: Event is most likely to be explained by the study rather than the subject's clinical state or other agents/therapies.

Possibly related: Event may be explained by the study procedure or by the subject's clinical state or other agents/therapies.

Probably not related: Event is most likely to be explained by the subject's clinical state or other agents/therapies, rather than the study procedure.

Definitely not related: Event can be fully explained by the subject's clinical state or other agents/therapies.

For causality assessments, events meeting the categories of definitely, probably, or possibly related will be considered to be related to study.

8.6.1.3 Assessments and Documentation of Adverse Events

Attention shall be paid to the occurrence of AEs for the duration of subject participation. Events occurring prior to Visit 2 (day of Tc 99m tilmanocept administration) will be recorded in the subject's medical history unless determined to be related to the study procedure. Untoward medical events beginning on Visit 2 (day of Tc 99m tilmanocept administration) through the completion of the Follow-up Phone Call will be reported as adverse events. Thus, subjects should be closely observed by the investigator both during and after the evaluation.

Any AE (observed, volunteered, or elicited) should be recorded in detail in the source documentation.

The following information is required:

- The **date and time of onset** of any AE.
- The duration (the entire duration of an event or symptom, calculated from date of onset to date of end, if not recorded directly).
- The seriousness of the AE will be assessed by the investigator. If the investigator deems that an AE qualifies as an SAE, a special form provided by the sponsor should be completed and the event must be immediately reported to the sponsor. A definition of SAEs is provided in [Section 8.6.1.5](#).
- The maximum intensity (mild, moderate, or severe).
- Whether drug treatment was administered for the event, any specific drug treatment must be documented.
- The relationship of the AE to the investigational product and to study conduct (for definitions, see above).

The **outcome** of the AE (resolved, resolved with sequelae, not resolved, unknown, death).

AEs will be coded according to an internationally recognized dictionary (Medical Dictionary for Regulatory Activities [MedDRA]).

8.6.1.4 Expected Adverse Events

Investigational Product-Related Risks

In all completed studies of Lymphoseek involving 553 subjects, only three events (breast pain and injection site pain reported by subjects with breast cancer and injection site irritation reported by a subject with head and neck squamous cell cancer) were deemed definitely related to the administration of Lymphoseek by the investigator. The most common adverse reactions (incident <1%) have been lack of effect (<0.067%), injection site pain (<0.02%) and rash (<0.02%).

In addition to the Lymphoseek pre-approval clinical studies, post-marketing surveillance shows that Lymphoseek has been administered to more than 250,000 patients with not a single drug-related SAE. Routes of administration include subcutaneous, intradermal, and peritumoral.

In Tc 99m tilmanocept trials for indications beyond lymphatic mapping and SLNB, there have been approximately 20 SC and 60 IV administrations of Tc 99m tilmanocept, and no SAEs or ADRs have been reported to date.

Adverse events from the radioactive dose are not expected, since the applied radiation doses are far below doses that can cause acute effects in human tissues.

Precautionary Measures

Special precautionary measures are not considered necessary for this study. In case of emergency, standard emergency procedures will be employed.

Unexpected Adverse Events

An unexpected adverse event is defined as an adverse reaction that in nature and severity is not consistent with the applicable product information (e.g., Investigator's Brochure). Any adverse experience that is not listed in the current Investigator's Brochure or which is, with regard to the specificity or severity, not consistent with the risk information shall be regarded as unexpected.

Examples would be (a) acute renal failure listed in the Investigator's Brochure with a subsequent new report of interstitial nephritis and (b) hepatitis with a first report of fulminant hepatitis. "Unexpected" as used in this definition refers to an adverse drug experience that has not been previously observed and included in the Investigator's Brochure, rather than from the perspective of such experience not being anticipated from the pharmacological properties of the investigational product.

8.6.1.5 Serious Adverse Events

Definition of Serious Adverse Events

Definition

The following SAE definition is based on ICH guidelines and the final rule issued by the Food and Drug Administration (FDA) and effective 06 Apr 1998.

An SAE is classified as any untoward medical occurrence that at any dose:

- results in death, or

- is life threatening, or
- requires inpatient hospitalization or prolongation of existing hospitalization, or
- results in persistent or significant disability/incapacity, or
- is a congenital anomaly/birth defect, or
- is an important medical event (see paragraphs below).

The term ‘life threatening’ in the definition refers to an event in which the subject was at risk of death at the time of the event; it does not refer to an event that hypothetically might have caused death if it were more severe.

Medical and scientific judgment should be exercised in deciding whether it is appropriate to report an AE as serious also in other situations, such as important medical events that may not be immediately life threatening or result in death or hospitalization but may jeopardize the subject or may require intervention to prevent one of the other outcomes listed in the definition above. These should also usually be considered serious. Examples of such events are intensive treatment in an emergency room or at home for allergic bronchospasm or blood dyscrasias or convulsions that do not result in subject hospitalization.

Actions and reporting obligations in case of serious adverse events

The investigator should take appropriate diagnostic and therapeutic measures to minimize the risk to the subject.

If any SAE occurs over the course of the study, investigators or other site personnel will inform Navidea Biopharmaceutical representatives within one day (i.e., within 24 hours) of becoming aware of the SAE. Written notification of the SAE will be emailed to Navidea Biopharmaceuticals Pharmacovigilance at [contact]. For fatal or life-threatening adverse events where important or relevant information is missing, active follow-up is undertaken immediately.

Pregnancy will have the same time reporting obligations to the sponsor as SAEs. Upon notification, Navidea will provide a form for collection of pregnancy information.

All SAEs must also be recorded on the Adverse Event eCRFs.

Notification of the IRB(s)

The sponsor and/or the investigator will notify the IRB(s) about all relevant events (e.g., SAEs and Suspected, Unexpected, Serious Adverse Reactions [SUSARs]) according to all applicable regulations.

Notification of the authorities

The sponsor will process and report all relevant events (e.g., SAEs, SUSARs) to the authorities according to all applicable regulations.

Sponsor’s notification of the investigators

The sponsor will inform all investigators about reported relevant events (e.g., SAEs, SUSARs) according to all applicable regulations.

8.6.2 Further Safety Assessments

8.6.2.1 Physical Exam

A complete physical examination at screening will be conducted according to the Schedule of Study Events (see [Appendix 1](#)). Height and body weight will be collected.

Physical examinations will be performed for the following body systems:

- General Appearance
- Skin/dermatological
- Eyes, ears, nose, throat
- Head and neck (including thyroid)
- Lungs
- Heart
- Abdomen (liver, kidney, spleen, gastrointestinal)
- Lymph nodes
- Musculoskeletal
- Nervous system

8.6.2.2 Electrocardiogram

A standard 12-lead electrocardiogram (ECG) will be obtained at screening and within 30 minutes after investigational product injection. The ECG will be measured with the subject in a resting position for at least 1 minute. No continuous ECG monitoring will be required. At a minimum the heart rate, QRS, PR and QT intervals will be collected. QTc will be calculated using the Fridericia formula.

On-site investigator's responsibilities

The immediate cardiac safety of the subject will be ensured by the on-site qualified physician. Any 12-lead ECG intervals, waveform abnormalities, and rhythm changes that are clinically significant in that they result in a change in subject management will be considered an AE. In the case of an SAE, once SAE notification is decided upon, investigators are required to follow the procedure described for SAE notification and document abnormal ECG findings (intervals and waveforms). Any interval data or abnormal waveform finding that resulted in an AE (i.e., change of patient management) must be followed to normalization or stabilization.

Each 12-lead ECG tracing must be signed and dated and stored in the subject's source documentation.

8.6.2.3 Vital Signs

Vital signs comprise the measurement of body temperature, heart rate, respiration, and systolic and diastolic blood pressure. All measurements will be taken after the subject has been in a resting position for at least 1 minute.

Vital signs will be measured at screening and within 30 minutes before investigational product injection, and within 30 minutes post-injection.

Any clinically significant change from screening (worsening) that results in a change in subject management will be considered an AE and will be recorded on the AE page of the CRF.

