5.3 Treatment Assignment

In this prospective, single center, open-label, non-randomized, dose-escalation, comparative, safety study, Cohort 1 subjects will receive an IV administration of 100 μ g/ 5 mCi Tc 99m tilmanocept. Cohort 2 subjects will receive an IV administration of 100 μ g/ 10 mCi Tc 99m tilmanocept. Cohort 3 subjects will receive a SC and an IV administration of 200 μ g/ 5 mCi Tc 99m tilmanocept approximately one week apart. Cohort 1 will be the starting dose group. Four subjects will be enrolled into Cohort 1.

If one of the four Cohort 1 subjects experiences a noxious pharmacologic activity/an ADR, two more subjects will be treated at the same tilmanocept mass dose and same radiolabel level as the subject with the ADR. If 2 out of 4 or 3 out of 6 subjects experiences a noxious pharmacologic activity/an ADR in

Cohort 1, the maximum tolerated dose (MTD) cannot be determined. If no additional noxious pharmacologic activities/ADRs are observed in the expanded cohort, the dose escalation will continue with Cohort 2. If one additional noxious pharmacologic activity/ADR is observed, the current dose will be deemed the MTD. If more than one additional pharmacologic activity or ADR is observed in the expanded cohort, the previous dose will be deemed the MTD.

If no noxious pharmacologic activities/ADRs are experienced in Cohort 1, Cohort 2 will be open for enrollment.

Dose escalation will continue until the MTD is found or until Cohort 3 is reached with only one ADR or without any ADRs. The maximum tolerated dose is defined as the highest dose level at which no more than 33% of subjects experienced an ADR. Visual representation of the dose escalation scheme may be found in Appendix 2.

NOTE: Adverse Drug Reaction

An Adverse Drug Reaction (ADR) includes all noxious and unintended responses to a medicinal product related to any dose or dose regimen. The phrase “responses to a medicinal product” means that a casual relationship between a medicinal product and an adverse event is at least a reasonable possibility, i.e. the relationship cannot be ruled out.

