8.6.2.4 Clinical Laboratory Parameters for Screening and Safety

Clinical laboratory tests to be evaluated in this study include hematology, serum chemistry, and urinalysis. Clinical laboratory tests will include the following as defined in Table 2.

Table 2. Clinical Laboratory Parameters

Hematology	Leukocytes, hemoglobin (Hgb), hematocrit (HCT), neutrophils, eosinophils, basophils, lymphocytes, monocytes, red blood cells (RBC), platelets
Serum chemistry	Aspartate aminotransferase (AST), alanine aminotransferase (ALT), alkaline phosphatase, total bilirubin, creatinine, chloride, potassium, sodium, total protein, albumin, globulin, carbon dioxide (CO ₂), blood urea nitrogen (BUN)
Urinalysis	pH, specific gravity

The site laboratory will provide the necessary supplies to collect the blood and urine samples.

All laboratory reports must be promptly reviewed for clinical significance by the investigator, and upon review, initialed and dated by the investigator.

Good clinical practice would suggest that a copy of the laboratory results also be provided to the subject's referring physician.

Any change in a laboratory value, which results in a change in subject management (additional controls or treatment required), will be reported as a clinically significant change. Clinically significant changes in laboratory parameters, which are not the result of laboratory error, are to be recorded as AEs.

Any clinically significant changes in laboratory values are to be followed up with repeated tests at appropriate intervals (as determined by the investigator) until the values return to baseline level or until the abnormality is explained by the investigator.

The expected amount of blood to be withdrawn is shown in [Table 3](#).

Table 3. Approximate Amount of Blood Withdrawn

Time point of examination	Amount of blood taken
Laboratory examination (Screening)	10 mL
Laboratory examination (Post-IV Imaging)	10 mL
Laboratory examination (Post-SC Imaging: Cohort 3 only)	10 mL
Total	20 mL (Cohort 3: 30 mL)

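### The ECG rule, and less tightly the vital-sign and laboratory rules, tie AE status to a change in management, which the general AE and ADR definitions do not, so some measured reactions may go uncounted as ADRs

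*Protocol*

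**What the plan says.** **General standard.** Protocol 8.6.1.1 says an AE can be "any unfavorable and unintended sign (including an abnormal laboratory finding), symptom, or disease temporally associated" with use of the product, and asks for all untoward occurrences from Day 1 to the follow-up call to be reported. Protocol 8.6.1.2 gives short-lived, well-tolerated events a grade of their own (mild). Protocol 5.3 says an ADR "includes all noxious and unintended responses to a medicinal product related to any dose or dose regimen", provided that a causal link between the product and an adverse event cannot be ruled out.

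**Parameter-specific standard.**
- ECG (8.6.2.2): findings that are "clinically significant in that they result in a change in subject management will be considered an AE". The same section later speaks of a finding "that resulted in an AE (i.e., change of patient management").
- Vital signs (8.6.2.3): "Any clinically significant change from screening (worsening) that results in a change in subject management will be considered an AE".
- Laboratory (8.6.2.4): a change "which results in a change in subject management (additional controls or treatment required), will be reported as a clinically significant change". It then adds: "Clinically significant changes in laboratory parameters, which are not the result of laboratory error, are to be recorded as AEs".
- Section 8.6.1.1 itself contains a sentence close to the vital-sign one, about the worsening of a condition since screening.

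**Use of the count.** Protocol 9.2 computes the primary endpoint as the proportion of subjects with an ADR. Protocol 5.3 uses noxious pharmacologic activity or ADRs to decide on expansion, escalation and the MTD. In the SAP, the ADR flag is a column of the adverse event listing (Data Listing 8), and Table 20 tabulates ADRs from MedDRA-coded adverse events.

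**The concern.** An asymptomatic ECG, blood-pressure or laboratory change that resolves without action meets the general AE definition. If it is judged related, it also meets the ADR definition. Under the ECG rule it is not an AE, and a reader of the vital-sign and laboratory rules could conclude the same. Staff reviewing a tracing or a laboratory report would naturally turn to the section on that measurement.

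Subjects receive one injection, or two in Cohort 3, so there is little ongoing dosing to alter in response to such a change. At stake are the primary endpoint, which could be biased downward, and the escalation decision, which in a cohort of four can turn on one event.

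**Working it through.** **1. The provisions side by side**

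| Provision | Management condition? | How tight |
|---|---|---|
| 8.6.1.1, general AE definition and reporting rule | No | – |
| 8.6.1.2, mild grade | No | – |
| 5.3, ADR definition | No | – |
| 8.6.2.2, ECG | Yes | A definition: significance is explained by, and AE equated with, a change in management |
| 8.6.2.3, vital signs, and the similar sentence in 8.6.1.1 | Yes | Sufficient condition; no word such as *only* |
| 8.6.2.4, laboratory | Yes | A management change makes the result clinically significant, and clinically significant changes are AEs; the investigator must also review every report for clinical significance |

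No provision says which standard prevails.

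**2. One case under both readings.** Suppose a post-injection ECG shows an interval change that the investigator thinks may be drug-related. The subject has no symptoms and nothing is done. Under 8.6.1.1 and 8.6.1.2 this is a mild AE, and under 5.3 it is an ADR. Under 8.6.2.2 it is not an AE. Two investigators who each follow the protocol could record it differently.

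**3. Path to the endpoint.** The ADR note in 5.3 presupposes an adverse event, and Data Listing 8 has one line per AE with the ADR flag on it. A change that was not entered as an AE has no line to flag, so it cannot reach Table 20. It would remain in the vital-sign, laboratory and ECG summaries and shift tables (SAP 5.0), which do not feed the primary endpoint or the rule in 5.3.

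**4. Plausibility.** Protocol 1.3.1 reports minimally higher, dose-related AST values in rats at 0.75 and 1.5 mg/kg that resolved by the end of recovery. These doses are far above the human one (200 µg / 70 kg ≈ 2.9 µg/kg, using the protocol's 70 kg). This shows the kind of finding at issue, not its frequency in this trial.

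**5. Sensitivity of the escalation rule.** The plan's one design figure is reproduced (4 + 4 + 6 = 14) but has no bearing here. Let p be the true per-subject rate of drug-related reactions and c the share recorded as ADRs, so that q = p × c. **Both are assumptions; the documents give neither.** Under 5.3, Cohort 1 escalates if 0 of 4 have an ADR, or if 1 of 4 does and then 0 of the 2 added subjects do:

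P(escalate) = (1−q)^4 + 4q(1−q)^3 × (1−q)^2

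| p | c = 1 | c = 0.75 | c = 0.5 | c = 0.25 |
|---|---|---|---|---|
| 0.10 | 0.892 | 0.935 | 0.969 | 0.992 |
| 0.20 | 0.672 | 0.788 | 0.892 | 0.969 |
| 0.33 | 0.380 | 0.560 | 0.754 | 0.923 |
| 0.50 | 0.125 | 0.296 | 0.554 | 0.843 |

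For p = 0.33 and c = 0.5, q = 0.165: 0.835^4 + 4 × 0.165 × 0.835^5 = 0.486 + 0.268 = 0.754.

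The chance of seeing at least one ADR in 14 subjects is 1 − (1−q)^14. At p = 0.10 it falls from 0.771 (c = 1) to 0.512 (c = 0.5). The table shows that the rule is sensitive to under-recording. It does not estimate how much there would be.

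**The case against.** A reader might infer that these changes become AEs only if management changes, so that a transient reaction needing no action can never be an ADR. The documents do not support that, and the case against it is strong.

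- **Sufficient, not necessary.** The vital-sign sentence says what will count and excludes nothing. Its near-twin in 8.6.1.1 is followed at once by the instruction to report all untoward occurrences, so it can be read as an addition to the general rule. This stands for vital signs. It does not rescue the ECG text, which is worded as a definition.
- **The laboratory rule is already wider.** It requires investigator review for clinical significance and explains management as extra controls or treatment. If that gloss carries over to the other sections, a repeat ECG or added observation would also qualify. This stands, but the carry-over is not written anywhere.
- **Symptomatic reactions are untouched.** Nausea, flushing or injection-site pain fall outside 8.6.2.2 to 8.6.2.4. This stands and confines the point to asymptomatic measured changes.
- **Escalation has other safeguards.** The synopsis places a safety review before each new cohort and does not confine it to coded AEs. The trigger in 5.3 also names noxious pharmacologic activity beside ADRs. This stands in part: the review could see the change, but that term is not defined and 9.2 counts ADRs alone.
- **A clinical-significance threshold is itself narrower than the general definition.** This stands, and the fix has to state the threshold once for all sections.

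**Conclusion.** The conflict is real. It is clearest for the ECG and weaker for vital signs and laboratory values. A site applying the parameter-specific text may leave an asymptomatic, drug-related change that needs no action unrecorded as an AE, and the change would then be missing from the primary endpoint and the escalation count. Such a change may be missed, but need not be, because a site applying 8.6.1.1 and 8.6.1.2 would record it. The measured values are kept in the summary and shift tables in any case.

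Any bias in the ADR proportion is downward. Its size cannot be computed, since the documents give no reaction rate and no recording share; the probabilities shown rest on assumed values of both. The conclusion assumes that ADRs are identified from AE records, as 5.3, Table 20 and Data Listing 8 indicate. It is a correctable inconsistency that should be resolved because it touches the primary endpoint; it is not evidence that reactions will be lost.

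**What to change.** Reconcile 8.6.2.2 to 8.6.2.4 and the management sentence in 8.6.1.1 with the general AE definition. State once, in 8.6.1.1, that an ECG, vital-sign or laboratory change the investigator judges clinically significant is recorded as an AE whether or not management changes, and have the three parameter sections refer to it. Remove the ECG wording that equates an AE with a management change. Keep the information as an eCRF attribute (management changed, Y/N). The usual causality assessment then decides whether the AE is an ADR.

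Add a sentence to Protocol 5.3 and 9.2 and to SAP 5.0 that this single standard feeds the ADR count for both the primary endpoint and escalation.

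The cost is protocol and SAP wording and one eCRF field. The downside is a few more recorded AEs and possibly a slightly higher ADR proportion. The change concerns recording only and alters no clinical procedure.
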